12.3 Contraception Requirements

WOCBP participants who choose complete abstinence must continue to have pregnancy tests, as specified in Schedule of Assessments.

WOMEN OF CHILDBEARING POTENTIAL DEFINITIONS AND METHODS OF CONTRACEPTION DEFINITIONS (WOCBP)

A woman is considered fertile following menarche and until becoming post-menopausal unless permanently sterile.

Women in the following categories are not considered WOCBP

- Premenarchal
- Premenopausal female with 1 of the following:
 - Documented hysterectomy
 - Documented bilateral salpingectomy
 - Documented bilateral oophorectomy
- Post-menopausal

Documentation of any of these categories can come from the site personnel's review of the female subject's medical records, medical examination, or medical history interview.

A postmenopausal state is defined as at least 12 months after last regular menstrual bleeding without an alternative medical cause.

• In case the last regular menstrual bleeding cannot be clearly determined, confirmation with repeated follicle stimulating hormone (FSH) measurements of at least > 40 IU/L (or higher per local institutional guidelines), is required.

Females on hormone replacement therapy (HRT) and whose menopausal status is in doubt will be required to use 1 of the non-estrogen hormonal highly effective contraception methods if they wish to continue their HRT during the study. Otherwise, they must discontinue HRT to allow confirmation of postmenopausal status by repeated FSH measurements before study enrollment.

CONTRACEPTION GUIDANCE FOR FEMALE PARTICIPANTS OF CHILD BEARING POTENTIAL

One of the highly effective methods of contraception listed below is required at the time of informed consent and until the end of relevant systemic exposure, defined as 28 days after the study vaccine administration.*

Highly Effective Contraceptive Methods (Failure rate of < 1% per year when used consistently and correctly)^a

Combined (estrogen- and progestogen-containing) hormonal contraception associated with inhibition of ovulation

- oral
- intravaginal

02 Dec 2019 Astellas Page 84 of 111

transdermal

Progestogen-only hormonal contraception associated with inhibition of ovulation

- oral
- injectable
- implantable

Hormonal methods of contraception containing a combination of estrogen and progesterone:

- vaginal ring
- injectables
- implants
- intrauterine hormone-releasing system
- intrauterine device

Bilateral tubal occlusion/ligation is considered as a highly effective contraception method.

Vasectomized partner: A vasectomized partner is a highly effective contraception method provided that the partner is the sole male sexual partner of the WOCBP and the absence of sperm has been confirmed. If not, an additional highly effective method of contraception should be used.

Sexual abstinence: Sexual abstinence is considered a highly effective method only if defined as refraining from heterosexual intercourse during the entire period of risk associated with the study vaccine. The reliability of sexual abstinence needs to be evaluated in relation to the duration of the study and the preferred and usual lifestyle of the participant. It is not necessary to use any other method of contraception when complete abstinence is elected.

CONTRACEPTION GUIDANCE FOR MALE PARTICIPANTS WITH PARTNER(S) OF CHILD BEARING POTENTIAL.

Male participants with female partners of childbearing potential are eligible to participate if they agree to the following during the study and until the end of relevant systemic exposure defined as 28 days after study vaccine administration.*

- Inform any and all partner(s) of their participation in a clinical drug study and the need to comply with contraception instructions as directed by the investigator.
- Male participants are required to use a condom during the study and until end of relevant systemic exposure defined 28 days after study immunization.
- Female partners of male participants who have not undergone a vasectomy with the absence of sperm confirmed or a bilateral orchiectomy should consider use of effective methods of contraception until the end of relevant systemic exposure, defined as 28 days after study immunization.

02 Dec 2019 Astellas Page 85 of 111

^{*} Local laws and regulations may require use of alternative and/or additional contraception methods.

^a Typical use failure rates may differ from those when used consistently and correctly. Use should be consistent with local regulations regarding the use of contraceptive methods for participants participating in clinical studies.

12.4 List of Excluded Concomitant Medications

Subjects must not use any of the following:

- Vaccines, blood product, immunosuppressants including systemic steroids (topical steroids will be allowed) from the day of study administration until 30 days postimmunization.
- Subjects may receive other routine immunizations at the 30-day follow-up visit after the completion of all study procedures at each site's discretion; however routine vaccines should not be given in less than 30 days post-study immunization.
- Acetaminophen and NSAIDs are allowed during the study, but not within 24 hours prior to immunization and collection of serum samples for immunogenicity.
- Use of any systemically absorbed antibiotics during the 30-day period prior to collection of the immunogenicity samples should be restricted unless clinically warranted (e.g., avoid prophylaxis) to avoid interference with the immunoassay. If a subject has been treated with any systemically absorbed antibiotics between day 1 and day 30, the 30-day follow-up visit should take place at least 7 days after the last dose of the antibiotics.

02 Dec 2019 Astellas Page 86 of 111

12.5 Laboratory Assessment

-	ry Assessment	
Laboratory Test	Visit	Parameters to be Analyzed
Hematology	Screening (Visit 1) or	Hemoglobin (HGB)
	Dosing (Visit 2),	Hematocrit (HCT)
	day 7 (Visit 3) and	• Erythrocytes (RBC)
	day 30 (Visit 4)	• Leukocytes (WBC)
		Differential WBC
		• Platelets (PLT)
Biochemistry	Screening (Visit 1) or	• Sodium (Na)
	Dosing (Visit 2),	• Potassium (K)
	day 7 (Visit 3) and	• Calcium (Ca)
	day 30 (Visit 4)	• Chloride (Cl)
		• Glucose (Gluc)
		Total cholesterol (TC)
		Triglycerides (TG)
		Blood Urea Nitrogen (BUN)
		• Creatinine (Cr)
		Creatine kinase (CK)
		Total protein (TP)
		• Uric acid (UA)
		• Albumin (Alb)
		C-reactive protein
Coagulation Profile	Screening (Visit 1) or	Prothrombin Time (PT)
Cougulation From	Dosing (Visit 2),	 Activated Partial Thromboplastin Time (aPTT)
	day 7 (Visit 3) and	Fibrinogen
	day 30 (Visit 4)	Tiothlogen
Hepatic Profile	Screening (Visit 1) or	Alkaline phosphatase (ALP)
-	Dosing (Visit 2),	Aspartate transaminase (AST)
	day 7 (Visit 3) and	Alanine transaminase (ALT)
	day 30 (Visit 4)	Gamma Glutamyl Transferase (GGT)
		Total bilirubin (TBL)
		• Lactate dehydrogenase (LDH)
Urinalysis	Screening (Visit 1) or	Using dipstick
	Dosing (Visit 2),	Protein
	day 7 (Visit 3) and	Glucose
	day 30 (Visit 4)	• pH
		Blood
		• Leukocytes
		Urobilinogen
		Bilirubin
		Ketones
		Nitrite
		Microscopy (Optional)
		• Casts
		• Crystals
		• Epithelial cells
		• Leucocytes
		• Erythrocytes
m 11 · · · ·		Bacteria
Table continued on next p	page	

02 Dec 2019 Astellas Page 87 of 111

Page 88 of 111

Sponsor: APGD- CONFIDENTIAL -

Laboratory Test	Visit	Parameters to be Analyzed
Pregnancy Test (females of childbearing potential only)	Screening (Visit 1) – serum, Dosing (Visit 2) – urine, Day 30 (Visit 4) – urine	Human Chorionic Gonadotropin (hCG)
Urine Drug Screening	Screening (Visit 1) or Dosing (Visit 2)	 Amphetamines Barbiturates Benzodiazepines Cannabinoids Cocaine
Virology	Screening (Visit 1) or Dosing (Visit 2)	 Anti-HAV (IgM) HBsAg Anti-HCV (reflex testing/HCV-RNA) Anti-HIV-1 and 2
Immunogenicity	Dosing (Visit 2) and day 30 (Visit 4)	Anti-biotinAnti-1500+0785IgG and OPA
Immunogenicity	Dosing (Visit 2), day 7 (Visit 3) and day 30 (Visit 4)	T-cell response (PBMCs)

02 Dec 2019 Astellas

12.6 Grading of Local Reactogenicity

Stage 1 Group 1 and Stage 2 Group 2 subjects will be asked to record the below local reactogenicity along with body temperature through day 7 following study immunization.

Local Reaction to Injectable Product	Mild (Grade 1)	Moderate (Grade 2)	Severe (Grade 3)	Potentially Life-threatening (Grade 4)
Pain Does not non-nar reliever activity or inter		Repeated use of non-narcotic pain reliever > 24 hours or interferes with activity	Any use of narcotic pain reliever or prevents daily activity	ER visit or hospitalization
Tenderness Mild discomfort to touch		Discomfort with movement	Significant discomfort at rest	ER visit or hospitalization
Erythema/Redness†* 2.5 – 5 cm		5.1 – 10 cm	> 10 cm	Necrosis or exfoliative dermatitis
Induration/Swelling;**	2.5 – 5 cm and does not interfere with activity	5.1 – 10 cm or interferes with activity	> 10 cm or prevents daily activity	Necrosis

ER: emergency room

02 Dec 2019 Astellas Page 89 of 111

[†] In addition to grading the measured local reaction at the greatest single diameter, the measurement should be recorded as a continuous variable.

[‡] Induration/Swelling should be evaluated and graded using the functional scale, as well as the actual measurement.

^{*} A measurement tool will be provided to the subjects to measure the diameter of the erythema/redness and induration/swelling.

12.7 Grading of Signs of Systemic Reactogenicity

Vital signs measurements will be monitored for reactogenicity through 1 hour postdose in all Stage 1 Group 1 and Stage 2 Group 2 subjects. Oral temperature will be recorded by the subjects daily through day 7 postimmunization.

Vital Signs†	Mild (Grade 1)	Moderate (Grade 2)	Severe (Grade 3)	Potentially Life-threatening (Grade 4)
Fever (°C)‡	38.0 - 38.4	38.5 - 38.9	39.0 - 40	> 40
(°F)‡	100.4 - 101.1	101.2 - 102.0	102.1 - 104	> 104
Tachycardia (bpm)	101 – 115			ER visit or hospitalization for arrhythmia
Bradycardia (bpm)§	50 – 54	45 – 49	< 45	ER visit or hospitalization for arrhythmia
Hypertension (systolic) (mm Hg)	141 – 150	151 – 155	> 155	ER visit or hospitalization for malignant hypertension
Hypertension (diastolic) (mm Hg)	91 – 95	96 – 100	> 100	ER visit or hospitalization for malignant hypertension
Hypotension (systolic) (mm Hg)	85 – 89	80 – 84	< 80	ER visit or hospitalization for hypotensive shock
Respiratory Rate (breaths per min)	17 – 20	21 – 25	> 25	Intubation

bpm: beats per minute; ER: emergency room

02 Dec 2019 Astellas Page 90 of 111

[†] Subject should be at rest for all vital sign measurements.

[‡] Oral temperature; no recent hot or cold beverages or smoking. Subjects will be provided with a digital thermometer to record oral temperature daily though day 7 postimmunization.

[§] When resting heart rate is between 60 and 100 bpm. Use clinical judgment when characterizing bradycardia among some healthy subject populations, e.g., conditioned athletes.

Stage 1 Group 1 and Stage 2 Group 2 subjects will be asked to record the below systemic reactogenicity through day 7 following study immunization.

Systemic (General)	Mild (Grade 1)	Moderate (Grade 2)	Severe (Grade 3)	Potentially Life-threatening (Grade 4)
Nausea/ Vomiting	No interference with activity or 1 – 2 episodes/24 hours	Some interference with activity or > 2 episodes/24 hours	Prevents daily activity, requires outpatient IV hydration	ER visit or hospitalization for hypotensive shock
Diarrhea	2 – 3 loose stools or < 400 g/24 hours	4 – 5 stools or 400 – 800 g/24 hours	6 or more watery stools or > 800 g/24 hours or requires outpatient IV hydration	ER visit or hospitalization
Headache	No interference with activity	Repeated use of non- narcotic pain reliever > 24 hours or some interference with activity	Significant; any use of narcotic pain reliever or prevents daily activity	ER visit or hospitalization
Fatigue	No interference with activity	Some interference with activity	Significant; prevents daily activity	ER visit or hospitalization
Arthralgia*	No interference with activity	Some interference with activity	Significant; prevents daily activity	ER visit or hospitalization
Myalgia	No interference with activity	Some interference with activity	Significant; prevents daily activity	ER visit or hospitalization
Illness or clinical AE (as defined according to applicable regulations) †	No interference with activity	Some interference with activity not requiring medical intervention	Prevents daily activity and requires medical intervention	ER visit or hospitalization

AE: adverse event; ER: emergency room; IV: intravenous.

Reference

Guidance for Industry titled "Toxicity Grading Scale for Healthy Adult and Adolescent Volunteers Enrolled in Preventive Vaccine Clinical Trials" issued by US Department of Health and Human Services Food and Drug Administration Center for Biologics Evaluation and Research on September 2007.

02 Dec 2019 Astellas Page 91 of 111

^{*} Stage 1, subjects will be questioned on day 7 visit if they experienced any joint pain/arthralgia through day 7 and if yes, the site personnel will report it as a clinical event using this grading scale. Stage 2 subjects will report arthralgia daily on electronic diary through day 7 postimmunization.

[†] Subjects will be questioned on day 7 if they experienced any other illness through day 7 postimmunization and if yes, the site personal will report it as a clinical event using this grading scale.

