- Immunogenicity data will be provided to the investigative site when available to support decision-making for the standard of care.
- k. Sample collection to test for serum anti-biotin antibodies should be repeated at the day 180 visit if tested positive on day 30. Biotin levels will be measured in the same sample if the sample is positive for anti-biotin.
- 1. All concomitant medications or therapies administered from the time the informed consent form (ICF) is signed through day 30 follow-up visit will be collected.
- m. Subject must be under direct supervision for the first 60 minutes following the injection. Local reactogenicity will be evaluated at 1 hour by site staff and entered into the electronic diary by the subject while on site. The subject will evaluate local and systemic reactogenicity symptoms except for joint pain/arthralgia as per Appendix 12.7 daily and record the results on an electronic diary daily through day 7 following the study immunization. On day 7, subject will be questioned if he/she experienced any other illness, which is not incorporated into the reactogenicity assessment, in the electronic diary.
- n. All observed or spontaneously reported AEs, inclusive of MAAEs, PIMMCs and NOCDs will be documented. AEs will be assessed at the study immunization visit, before and approximately 60 minutes after immunization. MAAEs will be reported through day 180. The investigator will avoid leading questions to influence reporting of AEs.

02 Dec 2019 Astellas Page 33 of 111

Table 3 Schedule of Assessments - Stage 2: Subjects 65 to 85 Years of Age and Received PCV13 Within a Year of Randomization (Group 3)

Assessments	Screeninga	Dosing	Follow-up
Visit Number	1	2	3
Visit Day (Window)	-40 to -3	1	30 (±2)
Informed Consent ^b	X		
Inclusion/Exclusion Criteria	X	Χţ	
Vaccine assignment ^c		Χţ	
Demographics	X		
Medical History ^d	X	Χţ	
Physical Examination ^e	X	Χţ	X
Routine 12-lead ECG	X	Χţ	X
Virology ^f	X		
Height, Body Weight	X		
Study Immunization		X	
Vital Signs (blood pressure, pulse rate, body temperature) ^g	X	Χţ	X
Clinical Laboratory Tests (hematology, biochemistry, coagulation profile, hepatic profile, urinalysis) ^h	X	X†‡	X
CCI			
Serum sample for Immunogenicity		Χţ	X
Prior/Concomitant Medication ^j			\rightarrow
AEs^k	<		
SAEs ^k			\rightarrow
MAAEs including PIMMCs and NOCDs ^k			\rightarrow

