5.4.3 Reactogenicity

Subjects will remain at the study site 60 minutes after the injection for safety evaluation. Subjects may be discharged after 60 minutes at the discretion of the investigator. Local and systemic reactogenicity will also be reported for each of 7 consecutive days following the study injection.

Reactogenicity will be assessed using solicited adverse reactions from the time of immunization (day 1) up to 7 days postimmunization. These include local and systemic reactions with a protocol-specified predefined grading scale (see [Appendix 12.6 Grading of Local Reactogenicity; Appendix 12.7 Grading of Signs of Systemic Reactogenicity; and Appendix 12.8 Grading of Laboratory Abnormalities]). Local reactions are pain, tenderness, redness/erythema and swelling/induration. Systemic reactions are nausea/vomiting, diarrhea, headache, fever, fatigue, joint pain or arthralgia and muscle discomfort or pain/myalgia. The daily maximum measurement of local and systemic reactogenicity signs will be recorded by the subject during the 7-day period using an electronic subject electronic diary. For Stage 1, subjects will be questioned at the day 7 visit if they experienced any joint pain/arthralgia through their day 7 visit postimmunization. If their response is yes, they will be asked to provide the degree of severity using a 4-category grading scale from 1 (no interference with activity) to 4 (ER visit or hospitalization) as per Appendix 12.7. For Stage 2, assessments of joint pain/arthralgia will be collected daily through day 7 using the electronic diary. All subjects will be questioned if they experienced any other illness through day 7 postimmunization on their day 7 visit. Reactogenicity reactions will be reported as Clinical Events. If the reactogenicity reaction extends beyond 7-day period or if serious, it will be recorded as an AE, and followed until resolution or deemed medically stable. Subjects will be instructed to contact the site during the 7 consecutive days following an injection to report any reaction \geq grade 2. All local and systemic reactions \geq grade 3 require confirmation by a health care professional.

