5.5 Adverse Events and Other Safety Aspects

5.5.1 Definition of Adverse Events

An AE is any untoward medical occurrence in a subject administered a study vaccine, and which does not necessarily have to have a causal relationship with this immunization. An AE can therefore be any unfavorable and unintended sign (including an abnormal laboratory finding), symptom, or disease (new or exacerbated) temporally associated with the use of a medicinal product whether or not considered related to the medicinal product.

In order to identify any events that may be associated with study procedures and could lead to a change in the conduct of the study, Astellas collects AEs even if the subject has not received study product. AE collection begins after the signing of the ICF and will be collected until 30 days after study vaccine administration or the subject is determined to be a screen failure.

Care will be taken not to introduce bias when detecting AEs and/or SAEs. Open-ended and non-leading verbal questioning of the subject is the preferred method to inquire about AE occurrences.

An abnormality identified during a medical test (e.g., laboratory parameter, vital sign, ECG data, physical exam) should be identified as an AE only if the abnormality meets 1 of the following criteria:

- Induces clinical sign or symptoms
- Requires active intervention
- Requires interruption or discontinuation of study medication
- The abnormality or investigational value is clinically significant in the opinion of the investigator.

MAAEs are AEs for which the subject has received medical attention by medical personnel, or in an emergency room, or which led to hospitalization. For each reported AE, the investigator will ask the subject if such medical attention has been received. In addition, the investigator will assess each MAAE if it constitutes a new-onset chronic disease (NOCD), defined as a MAAE which a) was absent at baseline, b) is not resolved at the follow-up telephone call, c) requires continuous medical care or attention. The investigator will also assess if any MAAE constitutes a PIMMC. PIMMCs are defined as any AEs of autoimmune

02 Dec 2019 Astellas Page 59 of 111

or auto inflammatory nature. The investigator will record MAAEs, NOCDs and PIMMCs in the AE eCRF.

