5.5.4 Criteria for Defining the Severity of an Adverse Event

The investigator will use the following definitions to rate the severity of each AE:

- Mild: No disruption of normal daily activities
- Moderate: Affect normal daily activities
- Severe: Inability to perform daily activities
- Potentially life threatening: Emergency room visit or hospitalization

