7.5.1 Adverse Events

A TEAE is defined as an AE observed after study immunization and up to 30 days postimmunization. SAEs will be monitored for up to 180 days postimmunization (Group 1 and Group 2).

For each immunization arm, the frequencies and percentages will be displayed for the following TEAEs (coded using the Medical Dictionary for Regulatory Activities [MedDRA]) by system organ class and preferred term:

- Overall
- Serious
- Related (yes or no) to study vaccine

The number and percentage of subjects with TEAEs, SAEs, AEs and AEs related to study vaccine will be summarized by system organ class, preferred term and immunization group. The number and percentage of AEs by severity will also be summarized. MAAEs including PIMMCs and NOCDs, if any, will be summarized. All AEs will be listed.

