Each local and systemic solicited reaction that continues beyond the first 7 days after the immunization or if it is serious will be recorded as an adverse event. The percentage of subjects who report pain, tenderness, redness/erythema, swelling or hardness/induration at the vaccination site, nausea, vomiting, diarrhea, headache, tiredness (fatigue), myalgia/muscle pain and arthralgia or other AE (not specified) will be summarized by grade (n, %) and overall regardless of grade (n,%).

Reactogenicity for each dose of ASP3772 will be compared to PCV13. The percentage of subjects who had 0, 1, 2, 3, 4 or 5 local reactions using a nonparametric CMH rank statistic. The systemic reactions will be compared in a similar way. The severity for each type of reaction will be compared for each dose of ASP3772 to PCV13 after assigning an increasing score to each severity and comparing the severity using a CMH statistic with scores=modridit.

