Diarrhea	2 – 3 loose stools or < 400 g/24 hours	4 – 5 stools or 400 – 800 g/24 hours	6 or more watery stools or > 800 g/24 hours or requires outpatient IV hydration	ER visit or hospitalization
Headache	No interference with activity	Repeated use of non-narcotic pain reliever > 24 hours or some interference with activity	Significant; any use of narcotic pain reliever or prevents daily activity	ER visit or hospitalization
Fatigue	No interference with activity	Some interference with activity	Significant; prevents daily activity	ER visit or hospitalization
Arthralgia*	No interference with activity	Some interference with activity	Significant; prevents daily activity	ER visit or hospitalization
Myalgia	No interference with activity	Some interference with activity	Significant; prevents daily activity	ER visit or hospitalization
Illness or clinical AE (as defined according to applicable regulations) †	No interference with activity	Some interference with activity not requiring medical intervention	Prevents daily activity and requires medical intervention	ER visit or hospitalization

AE: adverse event; ER: emergency room; IV: intravenous.

*: Stage 1, subjects will be questioned on day 7 visit if they experienced any join pain/arthritis through day 7 and if yes, the site personnel will report it as a clinical event using this grading scale. Stage 2 subjects will report Arthralgia daily on electronic diary through day 7.

† : Subjects will be questioned on day 7 if they experienced any other illness through day 7 post immunization and if any site personal will report it as a clinical event using this grading scale.

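### A short illness elicited at the Day 7 visit is sent to the clinical-event record with no stated route into the TEAE tables, on a grading row that leaves gaps against the AE severity scale

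*Protocol*

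**What the plan says.** **Towards a clinical event.** The last row of the systemic table in Protocol Appendix 12.7 covers illness in general. Its footnote says Group 1 and 2 subjects are asked at the Day 7 visit "if they experienced any other illness through day 7 postimmunization and if yes, the site personal will report it as a clinical event", on that table's grades. SAP Appendix C has the same footnote: "if they experienced any other illness through day 7 post immunization and if any site personal will report it as a clinical event". SAP 7.5.1, in its paragraph on solicited reactions, ends the list with "myalgia/muscle pain and arthralgia or other AE (not specified) will be summarized by grade".

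**When a clinical event becomes an AE.** Protocol 5.4.3 poses the Day 7 illness question and then says reactogenicity is reported as Clinical Events. It adds: "If the reactogenicity reaction extends beyond 7-day period or if serious, it will be recorded as an AE". SAP 6.2.1.6 has the same two conditions.

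**Towards an AE.** Protocol Table 2 footnote m says the subject is "questioned if he/she experienced any other illness, which is not incorporated into the reactogenicity assessment". Protocol 5.4.1 requires AEs that are seen or volunteered to be documented, and 5.5.1 defines an AE as any untoward medical occurrence after vaccination. Protocol 7.5.1 does not carve out the first week: "A TEAE is defined as an AE observed after study immunization and up to 30 days postimmunization". On medically attended events, 5.5.1 says: "For each reported AE, the investigator will ask the subject if such medical attention has been received". It also places MAAEs, NOCDs and PIMMCs in the AE eCRF.

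**Severity.** Protocol 5.5.4 grades AEs up to the third level on daily activity alone: "Severe: Inability to perform daily activities". The Appendix 12.7 illness row adds a medical-intervention condition at Grades 2 and 3.

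**The concern.** TEAEs, including MAAEs, are part of the primary endpoint in both stages. Days 1 to 7 are the period closest to vaccination and the period on which the DEC decides whether to escalate. If sites take the footnote as the complete instruction, unsolicited illness from that week sits with the reactogenicity data and does not appear among AEs. If other sites also complete an AE form, the TEAE table mixes two conventions. The SAP gives the programmer no rule for either case.

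The filing also matters to the DEC. The 10% unblinding check in Protocol 4.4.1 and the halting rule on unsolicited AE imbalance in 5.1.5 are both worded on AEs. The escalation criteria in 5.1.2 treat a severe AE and a Grade 3 reactogenicity event as separate items, so the criterion an early illness meets depends on where it is filed and on which scale. These passages need to be reconciled; nothing here says which rule is right.

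**Working it through.** The plan states no figure on this point, so there is none to reproduce. The check is a reading of the text, followed by an illustration.

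**1. Follow one event.** Take a non-serious illness that starts on Day 4, has gone by Day 7, and is elicited by the Day 7 question.

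| Text | Where it sends the illness |
|---|---|
| Protocol 12.7 and SAP Appendix C footnotes | Clinical event, reactogenicity table |
| SAP 7.5.1, solicited-reaction paragraph | Tabulated by grade with solicited reactions |
| SAP 7.5.2 | Describes clinical events as reactogenicity |
| Protocol 5.4.3, SAP 6.2.1.6 | AE only if serious or beyond 7 days, but worded for reactogenicity reactions |
| Protocol Table 2 footnote m | Outside the reactogenicity assessment |
| Protocol 5.4.1, 5.5.1, 7.5.1 | AE, and therefore TEAE |

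No text says the first route is additional to the last. The nearest guide is Protocol 5.4.2, where abnormal vital signs are clinical events up to Day 7 and AEs afterwards. There the two records are alternatives, and a site could reasonably read the illness footnote the same way. No SAP step carries clinical events into the TEAE tables.

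**2. What follows if it stays a clinical event.** It is absent from the TEAE tables. The medical-attention question is tied to reported AEs, so nothing triggers it. It is not counted in the AE-worded DEC checks. Group 3 is unaffected because it has no Day 7 visit.

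**3. Compare the scales.**

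| Activity | Medical intervention | Protocol 5.5.4 | Appendix 12.7 illness row |
|---|---|---|---|
| Partly limited | No | Moderate | Grade 2 |
| Partly limited | Yes | Moderate | No grade |
| Prevented | No | Severe | No grade |
| Prevented | Yes | Severe | Grade 3 |

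Two of the four combinations have no grade. The lowest and highest levels of the two scales agree in substance.

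**4. Illustrate the size.** From the documents: 99 subjects per Stage 2 ASP3772 arm, a 30-day TEAE window, and cohorts of 40 and 132. Assumed: a 30-day TEAE rate p of 10% to 30%, and a fraction f of affected subjects recorded only as clinical events, from 10% to 7/30 = 23%. The upper value of f is the first week's share of the window under uniform onset, as if every such event were lost. Expected subjects missing = 99 × p × f.

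- Low: 99 × 0.10 × 0.10 = 1.0.
- High: 99 × 0.30 × 7/30 = 6.9, so a true 30% would be reported as 23%.

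The 10% check needs 4 of 40 subjects in a Stage 1 cohort, and in Stage 2 10% of 132 = 13.2, so 14. If one event type truly affected 10% of a Stage 2 cohort, the binomial chance of reaching 14 is 0.45. It is 0.14 if 23% of those subjects are not counted as AEs. At a true 15% the figures are 0.94 and 0.67. For this check the 23% is an arbitrary share, because the DEC's data end at Day 7.

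**The case against.** The strongest reply is that the documents never say these illnesses are kept out of the AE data. The rule requiring seriousness or more than 7 days is written for reactogenicity reactions, and Table 2 footnote m puts other illness outside that category. The Appendix 12.7 row itself is labelled as covering a clinical AE. Under the general AE definition, a chest infection on Day 4 is an AE. The eCRF instructions, a separate document under Protocol 12.2.3, may tell sites to enter it as one. All of this stands. Loss from the TEAE tables is possible, not prescribed.

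Other limits also stand:

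- **MAAEs** are partly protected. Protocol 5.5.1 requires them in the AE eCRF, SAP 6.2.1.1 collects them from Day 1, and hospitalised cases are SAEs. The remaining gap is non-serious illness that received medical attention and resolved by Day 7.
- **NOCDs** are not at risk from short illness. They must be unresolved at the follow-up call.
- **The DEC** also reviews Day 7 reactogenicity data and may request any assignment. Its 10% check needs the same or a related AE, so assorted illnesses would seldom reach it.
- **The schedule footnotes** are weaker evidence than they look. Table 1 footnote o names joint pain in the same phrase, although that is a solicited reaction, so the phrase may mean only that the item is not in the diary.

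The reply does not remove the defect. The only specific instruction for this event names one destination, the general rules name another, and no text joins them. Protocol 5.4.2 supports reading the two as alternatives.

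**Conclusion.** The point holds as an unresolved conflict over where a Day 7 illness is recorded, together with a grading row that leaves two situations ungraded. A non-serious illness resolved by Day 7 may be missed from the TEAE tables, the per-AE medical-attention question and the AE-worded DEC checks. The size cannot be derived from the documents. The range of about 1 to 7 of 99 per arm rests wholly on the assumed TEAE rates and shares lost.

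A reader might infer that TEAE and MAAE rates will be understated, that the DEC will not see these illnesses, or that one vaccine is favoured. The documents do not support those readings: an AE entry is not excluded, the DEC receives reactogenicity data, and the routing is the same for ASP3772 and PCV13. Nor would every week-1 illness be lost. Serious ones are covered by SAE reporting, and persisting ones are covered if the 5.4.3 rule is applied to them. It should be corrected because the primary endpoint is involved and the correction is simple.

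**What to change.** 1. In Protocol 5.4.3 and Appendix 12.7 and in SAP Appendix C, state that any Day 7 illness that is not a listed solicited reaction is entered on the AE eCRF as an unsolicited AE, with 5.5.4 severity, a causality assessment and the MAAE and PIMMC questions.
2. Remove the unspecified other-AE item from the reactogenicity list in SAP 7.5.1.
3. Add a SAP derivation that includes any such clinical-event records already collected in the TEAE tables, and in the MAAE table where medical attention was received.
4. Reconcile the Grade 2 and Grade 3 wording of the illness row with Protocol 5.5.4.

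The illness row need not be deleted. Counting short solicited reactions as MAAEs is a separate design choice that this point does not require.

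The cost is wording in two documents and one derivation, with no extra visit or Day 7 question. TEAE counts may look slightly less favourable.
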